### 4.6. Data analysis plan:

**4.6a. Study Design Considerations:** The study design and data analysis will follow the CONSORT criteria for randomized controlled trials (RCTs). Participants will be randomly assigned to the treatment or control group as described in **Section 4.4b**. Randomization should produce groups that differ only by chance at baseline; nevertheless, the adequacy of randomization will be assessed by comparing the groups on all outcomes as measured at baseline. We will follow intention-to-treat (ITT) principles. While we anticipate some participants will not complete the intervention; we will continue to collect follow-up data from all randomized patients whether or not they complete the intervention program to which they are assigned. We anticipate no more than 10% of participants will have missing or incomplete follow-up data. To improve retention and reduce the risk of missing data, participants will be offered monetary incentives for completing follow-up assessments, regardless of whether they complete the intervention. In our recent studies of Veterans with disabilities, we were able to obtain follow-up data for up to 6 months in 92% of randomized participants. We have achieved this high follow-up rate by developing strong relationships with study participants, keeping them engaged and invested in the project, and making necessary accommodations to gather outcome data. While we do not anticipate differential attrition, we will compute the completion rate for each group (BEST and control) and compare completion rates to determine test for differences as a function of group. We will also compare baseline characteristics among those who have complete versus incomplete follow-up data to test for systematic attrition. To preserve the equivalency formed by randomization, ITT analyses will include all randomized participants for hypothesis testing. Since ITT analysis requires complete data, missing data will be imputed using multiple imputation. Sensitivity analyses will be performed comparing the ITT (with imputation) results to results for those with complete data (anticipated N=56). We have allowed for a 10% missing data rate in sample size computations. We anticipate randomizing 62 individuals (31 per group) to achieve a final total sample with complete outcome data at the 3-month followup of N=56 (28 per group). We do not anticipate additional attrition after 3 months since follow-up data beyond that time point will be gathered with remote telemonitoring.

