
**Overview of sample size computations:** Power computations were performed using the Stata power command. To determine the required sample size for the study, we determined the hypotheses for which we require the largest sample size. In this study, Aim 2 requires the largest sample size (n=56 with complete data; N=62 total randomized). We conducted the power analysis for Aims 1 assuming the sample size of N=56 required to address Aim 2. Given the exploratory nature of Aim 3, these tests were not considered in determining the required sample size for the overall study.

4.6b. Data Analysis and Sample Size Calculation for Aim 1: This aim examines the efficacy of the BEST program on PAP adherence. The main outcome will be the proportion of nights (out of 30 nights) with >4 hours of PAP use, as measured by the PAP machine itself. PAP adherence will be computed for the first 30 days (month 1), and for each subsequent 30-day period (months 2-12). All participants will be measured for at least 180 days, thus providing at least 6 months of data for all participants. PAP adherence rates beyond month 6 will be computed for participants who enrolled early enough to provide such data. Because adherence data will be gathered remotely using existing telemonitoring technologies in which PAP machines transmit use data to a cloud-based server, complete data is expected for each person. In an ongoing VA-funded study of PAP adherence being conducted by [name] research group, PAP adherence data or confirmed non-use has been obtained in 100% of participants using this method. The proportion of nights a patient uses PAP for 4 or more house will be computed by summing nightly scores (1=PAP used at least 4 hours; 0=PAP used less than 4 hours) and dividing the sum by the number of observations (i.e., 30 nights). Denoting  $\hat{p}_{ij}$  as the proportion of nights for person "i" in month "j", the sampling distribution of  $\hat{p}_{ij}$  will have an expected value equal to  $p_i$  (the true proportion who use PAP in the population in month "i") and the standard deviation of this sampling distribution is equal to  $sqrt(N*p_i *(1-p_i))$ . Further, based on the central limit theorem the sampling distribution of these monthly proportions,  $\hat{p}_i$  is expected to be normally distributed, justifying the use of normal theory statistical methods for the analysis of monthly PAP adherence.

[figure not shown]

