**Data Analysis for Hypotheses 2a-d.** These hypotheses will be tested using ANCOVA models to compare groups (BEST vs. control) for each of main outcome measured at post-treatment, after adjusting for baseline measurement of the outcome as a covariate. Compared to a "split-plot ANOVA" or an analysis of change scores, this strategy offers greater statistical power and better controls for possible baseline differences.

**Power Analysis for Hypotheses 2a-d. Table 7** shows the required sample size as a function of the standardized effect size and the correlation between posttest and baseline scores to achieve 80% power using a two-tailed alpha of 0.05. Cohen describes an effect size of d=0.8 as large, d=0.5 as medium, and d=0.2 as small. **Table 7** focuses on the combination of effect sizes and pretest-posttest correlations that would achieve power of .80. To evaluate plausible pretest-posttest correlations for the measures associated with hypotheses 2a-c, we assessed baseline to 4-month follow-up measures in a RCT of a sleep intervention for Veterans with disabilities. These are presented in detail below for each of the three hypotheses. **Table 7** shows that under the most pessimistic scenario (assuming no correlation between pre-test and post-test measures), this study has sufficient power to detect a large effect (*d*=0.75). As the purpose of this study is to find clinically meaningful effects (i.e., effects that tend to be large), this power analysis suggests sufficient power to detect such effects for all outcome measures. However, our prior research found very substantial pretest/posttest correlations (e.g., r=.75) which would permit detection of smaller effects (i.e., medium effects of d=0.50). Using the lower confidence limits still found substantial correlations (e.g., r=0.56) suggesting that this study will have the ability to detect all effects of d=0.63 or larger with a sample size of n=56 with complete 3-month follow-up data. To achieve this, we will randomize 62 subjects into intervention vs. control.

**Table 7**. Required total sample size as afunction of effect size and pre-test/post-testcorrelation for 80% power, alpha=.05.

Sample	Effect Size	Pretest/Posttest
Size	(Cohen's d)	Correlation
	d=0.50 (medium)	r=0.75
N=56	d=0.55	r=0.68
N-50	d=0.60	r=0.60
	d=0.63	r=0.56

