Hypothesis 2a: To estimate the pretest-posttest correlation, we used our prior research showing a baseline-4-month correlation for PSQI of r=0.74 (95% CI=[.56,.86], N=40). Choosing

d=0.65	r=0.50
d=0.70	r=0.36
d=0.75	r=0.00

the lower confidence limit (r=.56) implies sufficient power to detect an effect size of Cohen's d=.63 (an effect somewhat larger than a medium effect) with N=56 (**Table 7**). Choosing the observed correlation (r=.74) implies sufficient power to detect an effect size of Cohen's d=.50 (a medium effect). Assuming no correlation (r=0.00), the study could still detect an effect size of Cohen's d=.75 (a large effect).

Hypothesis 2b: In the same preliminary data we found the baseline-4-month correlation of instrumental measures of daily living (IADLs) was r=.81 (95% CI=[.67, .89[). Using the lower confidence limit suggests the ability to detect an effect of d=.55 (slightly larger than medium effect).

Hypothesis 2c: To inform the power for this hypothesis, we examined baseline-4-month correlations for PHQ9 and FSS in our prior work. The correlation for PHQ9 was r=.79 (95% CI=[.64,.89], N=40), and for FSS, r=.76 (95% CI=[.57,.87], N=36). Using a conservative approach (lowest lower confidence interval = 0.57), an effect size of 0.63 could be detected with a sample size of 56 (See **Table 7**). Assuming the lowest observed correlation (r=0.76), the study would have sufficient power to detect an effect of d=0.50 (a medium effect). Our **Preliminary Data** shown in section 3.6 indicate large treatment effects comparing a behavioral sleep program vs. attention-control in terms of FSS ( $\omega^2$ =64%) and PHQ9 ( $\omega^2$ =35%). We believe similarly "large" effects for these outcomes are likely in the proposed study.

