Hypothesis 2d: The main respiratory function outcomes are PFTs (i.e., upright and supine respiratory function/forces) measured at 3-months. While we have no prior data on pretest/posttest correlations for these measures, our prior research has found a the SD for FVC when measured sitting is 17.1, and 15.7 when supine. Considering a 12% change as clinically relevant, this implies an improvement, expressed as Cohen's d=.70 (sitting, 12/17.1) and d=.76 (supine 12/15.7). **Table 7** shows that there would be sufficient power to detect a 12% improvement in sitting respiratory function (corresponding to d=.70) given a correlation of r=.36 in from baseline to 3 months. Likewise, there would be sufficient power to detect a 12% improvement in supine respiratory function (corresponding to d=.76) regardless of the size of the correlation.

4.6d: Analysis plan for Exploratory Aim 3: This aim considers whether the BEST program is more effective for subgroups of patients such as those with depression, insomnia or bladder dysfunction. For categorical measures, grouping variables will be coded as 0/1. For continuous measures (such as ISI score), participants will be categorized into groups, using clinical cutoffs. If such cutoffs yield highly imbalanced groupings, we will consider a median split. For a given variable, each grouping variable will be interacted with treatment group and introduced into each analysis described in Aims 1 and 2. The test of the interaction will assess whether the treatment is more effective for one subgroup than another.

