Does Treatment Of Sleep-Disordered Breathing Improve Functional Outcomes In SCI?

Data Analysis Plan

NCT02830074

Approved Date April 2, 2020

DATA ANALYSIS PLAN

Data analysis plan for primary outcomes:

Data Analysis for Aim 1: This aim examines the effects of the BEST program on PAP adherence. The main outcome will be the number of nights (out of 90 nights) with >4 hours of PAP use (measured by the PAP machine itself). Hypothesis 1 will be assessed using a two-sample t-test to compare PAP use for the BEST program vs. control program. Because adherence data will be gathered remotely using telemonitoring technologies in which PAP machines transmit use data to a cloud-based server, complete data is expected for each person.

Data analysis for Aim 2: This aim compares outcome measures assessed at 3-months that are expected to improve as a result of the BEST program. These outcomes will be -- 1) Subjective Sleep Quality Measured by The Pittsburgh Sleep Quality Index (PSQI); 2) Quality of Life as Measured by WHO-QOL BREF Questionnaire, 3) Respiratory Function: Spirometry and Respiratory Muscle Force, 4) Functional Status as Measured by CHART Questionnaire, 5) Depressive Symptom Severity as measured by the Patient Health Questionnaire-9 (PHQ-9); 6) Fatigue Symptoms as measured by Flinders Fatigue Scale; 7) Sleepiness as measured by the Epworth Sleepiness Scale. For each outcome measure, a two-sample t-test will be used to compare PAP use for the BEST program vs. control program.

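### The SAP tests Aim 2 with unadjusted two-sample t-tests, but the sample size rests on baseline-adjusted ANCOVA; planned power of 80% at d=0.63 (r=0.56) becomes about 64% on raw scores or 69% on change scores

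*SAP*

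**What the plan says.** **Protocol, section 4.6c (analysis of Aim 2).** The stated method is: "These hypotheses will be tested using ANCOVA models to compare groups (BEST vs. control) for each of main outcome measured at post-treatment", with the baseline value of the outcome as covariate. The protocol prefers this to split-plot ANOVA or change scores because it gives more power and better control of baseline differences.

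**Protocol, section 4.6a (Overview of sample size computations).** The trial's size comes from this aim: "Aim 2 requires the largest sample size (n=56 with complete data"; 62 are to be randomized.

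**Protocol, section 4.6c (Power Analysis for Hypotheses 2a-d).** The underlined claim is that "this study will have the ability to detect all effects of d=0.63 or larger with a sample size of n=56". It uses r=0.56, the lower 95% confidence limit of the PSQI baseline-to-follow-up correlation. The fallback is that "under the most pessimistic scenario (assuming no correlation between pre-test and post-test measures), this study has sufficient power to detect a large effect", namely d=0.75.

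**SAP, Data analysis for Aim 2.** After listing seven outcomes assessed at 3 months: "For each outcome measure, a two-sample t-test will be used to compare PAP use for the BEST program vs. control program". There is no covariate, no mention of change from baseline, no reason for the different method and no power statement. The SAP is dated 2 April 2020 and the protocol 4 April 2019.

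**The concern.** The two documents name different tests for the same hypotheses, and the trial was sized on the one the SAP drops. The d=0.50 to d=0.70 rows of Table 7 all depend on removing the variance that baseline explains. Without the covariate that gain is lost in full (raw scores) or in part (change scores, which the protocol considered and rejected).

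At stake is the chance of missing a real medium-to-large effect on sleep quality, depression or fatigue in a trial with about 28 analysable participants per arm. The SAP also leaves the tested quantity open, so two analysts could follow it and report different results. Read literally it compares PAP use, which is the Aim 1 variable; this looks like a wording slip and does not affect validity.

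**Working it through.** **Inputs (protocol 4.6a and 4.6c).** 28 complete per arm, two-sided alpha 0.05, target power 80%, and Table 7's pairs of d and r. The outcome SD is set to 1, with equal variance at baseline and follow-up.

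**SD of the analysed quantity**
- ANCOVA: sqrt(1 − r²); at r=0.56, sqrt(1 − 0.3136) = 0.8285
- Change score: sqrt(2(1 − r)); at r=0.56, sqrt(0.88) = 0.938
- Raw 3-month score: 1

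**Reproducing the protocol's figure.** By the normal formula, n per arm = 2(1.960 + 0.842)² × SD² / d². For ANCOVA at d=0.63, r=0.56 this is 2 × 7.849 × 0.6864 / 0.3969 = 27.1, rounded up to 28 per arm, N=56. All seven rows of Table 7 return N=56 in this way, so the stated sample size is right for ANCOVA.

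**Power with 28 per arm.** Noncentral t, noncentrality = (d/SD) × sqrt(28/2); df = 53 for ANCOVA and 54 for the t-tests. At d=0.63, r=0.56 the noncentralities are:
- ANCOVA: 0.760 × 3.742 = 2.85
- Change: 0.672 × 3.742 = 2.51
- Raw: 0.63 × 3.742 = 2.36

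| d, r (Table 7) | ANCOVA | t-test, change | t-test, raw |
|---|---|---|---|
| 0.50, 0.75 | .793 | .738 | .451 |
| 0.55, 0.68 | .787 | .715 | .525 |
| 0.60, 0.60 | .787 | .693 | .597 |
| 0.63, 0.56 | .798 | .694 | .639 |
| 0.65, 0.50 | .787 | .666 | .666 |
| 0.70, 0.36 | .787 | .623 | .730 |
| 0.75, 0.00 | .787 | .496 | .787 |

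The normal approximation gives .812, .710 and .654 in the d=0.63 row. A simulation of 20,000 runs gave .789, .695 and .635.

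**Detectable d at 80% power, N=56 (noncentral t).** ANCOVA 0.63 (r=0.56) or 0.50 (r=0.75); change 0.71 or 0.54; raw 0.76 whatever r is (0.75 by the normal approximation).

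**Total N for 80% power at d=0.63, r=0.56 (noncentral t).** ANCOVA 58, change 72, raw 82.

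**If all 62 randomized had complete data (31 per arm).** At d=0.63, r=0.56: change .739, raw .685. Both are still below 80%.

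**Variance of the raw-score comparison relative to ANCOVA, 1/(1 − r²).** 1.46 at r=0.56; 2.21 at 0.74 (PSQI); 2.37 at 0.76 (fatigue); 2.66 at 0.79 (PHQ-9). The 0.76 is reported for FSS, taken here to be the fatigue scale because the protocol uses FFS and FSS interchangeably.

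**Baseline data.** Table 6 lists baseline collection of PSQI, WHOQOL-BREF, FVC, MIP, CHART, PHQ-9, FFS and ESS, so the covariate exists for every SAP Aim 2 outcome.

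**The case against.** **The loss depends on r and on the score tested.** At the correlations the protocol observed, a change-score t-test at d=0.63 has power .89 (r=0.74), .92 (r=0.76) and .95 (r=0.79). This stands: on change scores at those correlations, the d=0.63 claim survives. But the protocol planned on r=0.56, and the SAP's reference to outcomes assessed at 3 months favours raw scores, for which power is .64 at any r.

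**The trial expects large effects and already accepted d=0.75.** The protocol says it seeks effects that tend to be large. Raw-score power at d=0.8 is .84, and supine FVC (d=0.76) keeps .80. This stands too and limits the harm. The protocol nevertheless presents d=0.75 as its most pessimistic case, and on raw scores the SAP makes it the only case.

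**Sitting FVC is a weak example.** The claim is that "there would be sufficient power to detect a 12% improvement in sitting respiratory function (corresponding to d=.70) given a correlation of r=.36". The protocol has no data behind that correlation and names supine FVC and MIP as the key respiratory outcomes. Fair; the conclusion does not rest on this row.

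**The SAP may be a deliberate simplification.** It is later, and it also replaces the Aim 1 mixed model with a t-test. That is possible, but neither document says so, and a deliberate change still needs a reason and a restated detectable effect.

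**A single sentence may not settle everything.** WHOQOL-BREF yields four domain scores and respiratory function several measures. True, but the SAP's present wording leaves the same gap.

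**Conclusion.** The concern holds. The SAP's Aim 2 test does not deliver the power on which the protocol sized the trial. At N=56, d=0.63 and r=0.56, power is about 64% on raw 3-month scores or 69% on change scores, against 80% by ANCOVA. On raw scores only the d=0.75 fallback survives, including supine FVC at d=0.76.

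This is a loss of precision with no bias, and should be fixed before analysis. The raw-score figure does not depend on r; the ANCOVA and change-score figures do. The correlations are 4-month values from another trial, and the documents give none for WHOQOL-BREF, CHART, ESS or the respiratory measures. Confidence is high, because the conflict is in the text and the protocol's own N reproduces.

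**What to change.** Replace the last sentence of the SAP's Aim 2 paragraph with:

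> For each outcome listed above, the 3-month score will be compared between the BEST and control groups by ANCOVA adjusting for the baseline value of that outcome (protocol 4.6c), in all randomized participants, with multiple imputation of missing data (protocol 4.6a).

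This also replaces PAP use with the named outcomes. The imputation clause adds nothing new; protocol 4.6a already says "Since ITT analysis requires complete data, missing data will be imputed using multiple imputation". While editing, name the score for the multi-part outcomes; the protocol's outcome descriptions already specify the four WHOQOL-BREF domain scores, supine FVC and MIP. The t-test can stay as a sensitivity analysis.

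If the t-test is to remain primary, the SAP should say whether it uses raw or change scores, give the reason for leaving ANCOVA, and restate the detectable effect at N=56 (about d=0.75 on raw scores).

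The cost is one SAP sentence, plus the score names. No new data or participants are needed: baseline values are already collected, and both the ANCOVA and the imputation are already in the protocol.

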### 4.4. Procedures:

Once enrolled, participants will complete a baseline assessment at the sleep laboratory. All data will be collected by trained research personnel, using participant interview and monitoring in the sleep laboratory. Research staff will undergo structured training, including review of human subjects protection issues, emergency procedures, interviewing techniques, cultural sensitivity training, and in-depth instruction on data collection instruments and equipment. We have procedure manuals for all instruments and equipment to be used in this study. Adequate inter-rater reliability will be established and reassessed annually. The methods and instruments we have selected were chosen to minimize participant burden while maximizing reliability and validity. Whenever possible, we have used measures that have been studied in patients with SCI/D. As we have done in our preliminary studies, we will arrange for and provide transportation to the study site. Each participant will travel to the study site for 6 separate visits. The first two to gather baseline data, and the third to initiate the intervention Version Date: 3.6.2019

or control condition. The fourth and fifth visit will be to complete the 1-month and 3-month follow-up (**Table 2**). The final visit will be coordinated with participants to download their SD card at the 6 month mark from when they received the machine.

Table 2: Activities for each participant visit to the VAMC.

	Visit 1	Visit 2*	Visit 3	Visit 4	Visit 5	Visit 6
Screening and informed consent	$\checkmark$					
Questionnaire assessments and respiratory measures	$\checkmark$			$\checkmark$	$\checkmark$	
Attended polysomnography (PSG) or at-home sleep study*		$\checkmark$				
PAP titration study (intervention begins)**			$\checkmark$			
SD Card Download						$\checkmark$

\*During overnight sleep laboratory monitoring (7pm-7am) \*\*only for those with SDB

**4.4a. Baseline assessment:** Once enrolled (after informed consent), a battery of questionnaires (**Table 6**, **below**) assessing sleep, quality of life and functional status will be completed in interview format. Participants will then return to the sleep laboratory for overnight attended, in-lab PSG and pulmonary function tests. An athome sleep test will also be available to participants at their convenience.

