documented, and the total number of unscheduled calls will be computed. For telephone sessions, the interventionist will document whether the information was presented to the patient, caregiver, or both simultaneously. We have used this systematic checklist method our in prior research and have shown it correlates well with completion of the forms by an observer. While recording sessions and independently scoring them is more desirable, we have found that audio-recording is a barrier to participation in research for some Veterans, and we have therefore chosen to use this method instead. In addition, [name] (BEST program) and [name] (controls) will remain blinded to the content of the other intervention arm. This will also help to prevent "contamination" of the control group by components of the active treatment.

**4.4d. Post-intervention follow-up assessment:** Enrolled participants will be asked to return to the medical center and complete a post-intervention assessment (**Table 6**) three months after the beginning of PAP treatment. For those who are unable or unwilling to come to the facility, a research assistant will travel to their home and complete assessments at that location. If the individual lives more than 50 miles away or has relocated out of the area, the questionnaire data will be gathered over the telephone. We selected the 1-month and 3-month follow-up time frame as it strikes a balance between the desire to evaluate benefits of treatment while considering that longer follow-up intervals may decrease our ability to contact participants for re-assessment and that intervening health events may increase the variability in treatment response. Participants who complete the 3-month follow-up assessments will be compensated \$50 for their travel and time.

Table 6: Study variables and measurements	at each	assessment visit		Visit	
Descriptive and clinical measures		Measurement Instrument	Base- line	1m f/up	3m f/up
Age, race/ethnicity, marital status, educ.		Core demographics questionnaire	X		X
Self-reported comorbidities		Comorbidity Index 	Х		Х
Pain		Brief Pain Inventory 	Х	Х	Х
PTSD symptoms		PC-PTSD 	Х	Х	Х
Anxiety symptoms		Patient Health Questionnaire, GAD-769	Х	Х	Х
Sleep Measures		Measurement Instrument			
SDB severity (PSG)		Apnea/Hypopnea Index from PSG	Х		
Symptoms of restless legs syndrome		RLS questionnaire	Х		Х

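### The SAP tests Aim 2 with an unadjusted t-test at 3 months and states no analysis set or missing-data method, which departs from the protocol's ITT, multiple imputation and ANCOVA

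*SAP*

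**What the plan says.** **SAP, Data analysis for Aim 2 (approved April 2020).** Seven outcomes assessed at 3 months are listed, followed by the only statement of method: "For each outcome measure, a two-sample t-test will be used to compare PAP use for the BEST program vs. control program". No covariate, analysis population or handling of missing values is given. The SAP's one remark on completeness sits under Aim 1 and concerns PAP device data.

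**Protocol 4.6a (approved April 2019).** "ITT analyses will include all randomized participants for hypothesis testing", and "Since ITT analysis requires complete data, missing data will be imputed using multiple imputation". Complete cases (anticipated N = 56) are a sensitivity analysis. The variables in the imputation model are not stated.

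**Protocol 4.6c.** Aim 2 is analysed by ANCOVA on the post-treatment value with the baseline value as covariate. The protocol prefers this partly because it gives more power.

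**Protocol 4.4, 4.4d and Table 6.** "The fourth and fifth visit will be to complete the 1-month and 3-month follow-up". Table 6 marks PSQI, WHOQOL-BREF, PHQ-9, Flinders Fatigue Scale, Epworth, CHART, FVC and MIP at baseline, 1 month and 3 months. For participants who live more than 50 miles away or have moved out of the area, "the questionnaire data will be gathered over the telephone".

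**The concern.** The later document is shorter than the earlier one and specifies a weaker analysis. Three things are at stake.

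- **Power.** The protocol sized the trial on ANCOVA. An unadjusted t-test on the same 56 people does not have the power that was planned whenever baseline and follow-up are correlated.
- **Who is analysed.** A t-test with no missing-data rule uses whoever has a value. If the plan stays silent, the choice between completers and imputation can be made after results are seen.
- **Bias.** If loss differs by arm and is related to how participants fare, the completer comparison is distorted. The 1-month values are natural predictors of a missing 3-month score, and no written Aim 2 analysis names them.

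Read literally, the sentence also tests PAP use under every Aim 2 outcome, which would repeat Aim 1. This looks like a wording slip, but it is the only statement of the Aim 2 comparison.

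**Working it through.** **Inputs from the protocol.** Table 7 is built "to achieve 80% power using a two-tailed alpha of 0.05". The headline claim is that "this study will have the ability to detect all effects of d=0.63 or larger with a sample size of n=56". Under hypothesis 2a, "the lower confidence limit (r=.56) implies sufficient power to detect an effect size of" d = 0.63. Section 4.6a gives 62 randomized (31 per arm), 56 with complete data (28 per arm) and a 10% missing-data allowance.

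**1. Reproduce the plan's figure.** With ANCOVA, n per arm = 2(1.960 + 0.842)²(1 − r²)/d².
- At d = 0.63, r = 0.56: 2 × 7.849 × 0.6864 / 0.3969 = 27.1, rounded up to 28, so N = 56.
- The other six rows of Table 7 also round up to 28 per arm.
- 62 × 0.9 = 55.8, and 62 − 56 = 6 expected incomplete.

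The sample size therefore already assumes both the baseline covariate and 56 completers.

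**2. Power with and without the covariate, 28 per arm.** Noncentral t, 54 df, critical value 2.005.
- Without: noncentrality = 0.63 × √14 = 2.357; power 63.9%.
- With: 0.63/√0.6864 = 0.760; noncentrality = 0.760 × √14 = 2.845; power 79.8%.
- Difference: 15.9 points.

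The loss depends on r. The table uses other rows of Table 7:

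| d | r | t-test | ANCOVA |
|---|---|---|---|
| 0.50 | 0.75 | 45.1% | 79.3% |
| 0.63 | 0.56 | 63.9% | 79.8% |
| 0.70 | 0.36 | 73.0% | 78.7% |
| 0.75 | 0.00 | 78.7% | 78.7% |

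By the formula in step 1 with r = 0, an unadjusted test at d = 0.63 needs 2 × 7.849/0.3969 = 39.5, so 40 per arm or 80 completers.

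**3. What the 1-month values can add.** Let ρ be the partial correlation of the 1-month with the 3-month value given baseline. The documents do not give it, so 0.3 to 0.9 is assumed. Assume also that everyone missing at 3 months has a 1-month value. Effective N = 1/[(1 − ρ²)/56 + ρ²/62]. Power is at d = 0.63, r = 0.56, with the covariate.

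| ρ | effective N | power |
|---|---|---|
| 0 | 56.0 | 79.8% |
| 0.3 | 56.5 | 80.2% |
| 0.5 | 57.4 | 80.8% |
| 0.7 | 58.8 | 81.7% |
| 0.9 | 60.8 | 83.0% |

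The gain is 0.4 to 3.2 points. With all 62 values observed, power would be 83.8%.

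**4. Bias, as an illustration only.** Suppose 5% are lost in BEST and 15% in control, and those lost are 0.5 to 1 SD worse than completers in their arm. The completer difference then shifts by (0.15 − 0.05) × 0.5 to 1 = 0.05 to 0.10 SD, which is 8% to 16% of d = 0.63. Control completers would look too well, so a benefit of BEST would be understated; if those lost were better off, it would be overstated. No rate or deviation in this step comes from the documents.

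**The case against.** The strongest objection is that the SAP is silent, not contrary. A reader might infer that it restricts Aim 2 to completers and so reverses the protocol's ITT rule. It does not say that, and it does not withdraw section 4.6a. Multiple imputation followed by a t-test would satisfy both texts on missing data. This stands: dropping non-completers is the default of an unspecified t-test, not a stated rule. It does not rescue the covariate, because an unadjusted two-sample t-test is a different analysis from the protocol's ANCOVA.

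A reader might also infer that analysing completers cuts power from 83.8% to 79.8%. The documents do not support that. Power was planned on 56 completers, and 83.8% would need all 62 values observed, which no imputation or mixed model supplies.

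Nor can one say that the 1-month values are ruled out: the unspecified imputation model could include them. Table 6 names only FVC and MIP for respiratory function, so 1-month data are not shown for every measure that the SAP's broader wording could cover.

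On differential loss, the protocol expects none, plans to compare completion between arms, pays for follow-up regardless of intervention completion, and cites 92% follow-up in earlier work. Scheduled sessions are close to matched (six in Table 4, five in Table 5). The arms differ mainly in monitoring and the calls it triggers. These points make large bias less likely but do not replace a missing-data method.

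Telephone follow-up yields no spirometry, so respiratory outcomes may be missing more often. Home visits come first, however, no rate is given, and a participant too distant at 3 months may lack the 1-month test too.

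**Conclusion.** The point holds as an inconsistency between the two documents, with a better method already in the protocol. The SAP's Aim 2 sentence drops the baseline covariate, states no analysis set or missing-data method, and names the wrong outcome.

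The loss that can be computed from the plan's own figures is the covariate: about 16 points of power at d = 0.63 and r = 0.56. It is larger at the correlations the protocol observed in earlier work, and nil if r is zero. The protocol has no correlation for the respiratory measures, so the loss there is unknown.

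The missing-data part concerns about 6 of 62 participants. Its recoverable precision is small, and its value lies in keeping to ITT, fixing the choice in advance and guarding against differential loss. The size of any such bias cannot be derived from the documents. The SAP should be corrected before the Aim 2 data are analysed.

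**What to change.** Replace the SAP's Aim 2 sentence with:

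> Each Aim 2 outcome at 3 months will be compared between arms in all randomized participants by ANCOVA adjusted for the baseline value and level of injury (the randomization block), with missing values multiply imputed by a model that includes arm, the baseline value and the 1-month value; complete cases are a sensitivity analysis.

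This carries sections 4.6a and 4.6c of the protocol into the SAP and removes the reference to PAP use. Two elements are new: level of injury, which section 4.4b uses to block the randomization, and a stated imputation model. For respiratory measures with no 1-month value, the imputation model should say what it uses instead.

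A repeated-measures mixed model over months 1 and 3, with baseline, level of injury and treatment by visit, is an acceptable alternative. It is a different analysis, so one of the two should be named in advance.

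The cost is one sentence of SAP text and slightly more programming. No extra visits, data or participants are needed. The missing-at-random assumption is one that the protocol's imputation already makes.
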